7.2.5.3. Exploratory Endpoints

Analysis of exploratory efficacy endpoints will be detailed in the SAP.

7.2.6. Pharmacodynamic Analysis

Summary tables and graphical displays of observed values, changes and percentage changes from baseline in PD biomarkers (TTR and vitamin A) will be presented.

7.2.7. Pharmacokinetic Analysis

Pharmacokinetic analyses will be conducted for ALN-TTRSC02 and patisiran using non-compartmental method. PK parameters will be calculated using a validated version of Phoenix® WinNonlin.

Population pharmacokinetic analysis will be performed to describe the plasma pharmacokinetics using Phoenix NLME (Version 1.1 or later) or a similar software, such as NONMEM. The impact of relevant covariates, such as, weight, sex, race, age, renal function, and hepatic function on plasma PK will be evaluated. Summary tables and figures and inferential statistics will be generated.

7.2.8. Safety Analyses

A summary of study drug exposure, including the durations of exposure and the proportions of patients with dose modifications will be produced.

Prior and concomitant medications will be coded using the World Health Organization (WHO) Drug Dictionary. Results will be tabulated by Anatomical Therapeutic Chemical Classification System (ATC) and Preferred Term.

Adverse events will be summarized by MedDRA system organ class and preferred term. The number and percentage of patients experiencing AEs after the first dose of the study drug will be summarized. Separate tabulations will be produced for treatment-related AEs, SAEs, and discontinuations due to AEs. By-patient listings will be provided for deaths, SAEs, and events leading to discontinuation of treatment.

Descriptive statistics will be provided for clinical laboratory data, 12-lead ECG interval data and vital signs data, presented as both actual values and changes from baseline over time

Laboratory shift tables from baseline to worst values will be presented. Baseline will be defined as the last observation on or prior to Study Day 1.

Other safety summaries will be presented as appropriate. Further details will be specified in the SAP.

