The TTR percent reduction through Month 18 will be derived as the average trough TTR percent reduction from Month 6 to 18 which is the steady state period for both ALN-TTRSC02 and patisiran. A Hodges-Lehmann method stratified by previous TTR stabilizer use (yes vs no) will be used to estimate the 95% confidence interval (CI) for the median difference between the ALN-TTRSC02 and patisiran groups in this study. Non-inferiority will be declared if the lower limit of the 95% CI for the treatment difference is greater than -10% . A sensitivity analysis will be conducted to compare the TTR percent reduction between the ALN-TTRSC02 group from this study and the pooled patisiran groups from this Phase 3 study and the APOLLO study.

Overall type I error control for secondary endpoints will be achieved by a hierarchical testing procedure.

The analysis of exploratory efficacy endpoints will be described in the SAP.

Safety data will be summarized descriptively.

Figure 1: Study Design

[figure not shown]
[figure not shown]
[figure not shown]

Table 1: Schedule of Assessments – Screening through Treatment Period Month 9

		Screening	Baseline				Treatment Period												Month 9 Efficacy
		V1	V2	V3	Pre-dose	Post-dose													
Study Day	Note				Day 1	D22	D43	D64	D85	D106	D127	D148	D169	D190	D211	D232	D253	D254-D273	
Study Week					0	3	6	9	12	15	18	21	24	27	30	33	36	36-39	
±Visit Window						0	±3D	±3D	±3D	±3D	±3D	±3D	±3D	±3D	±3D	±3D	±3D	±3D	NA ^a
Informed Consent	Section 6.1	X																	
Medical Records Release Form (optional)	Section 6.1	X																	
Inclusion/Exclusion	Section 4.1; Section 4.2	X	X																
Demographics and Medical/Disease History	Section 6.1.3	X	X	X															
Physical Exam (PE)	Symptom-directed PE unless specified as Full see Section 6.5.3	X PE Full		X					X				X					X PE Full	
Vital signs; Weight	Section 6.5.1; Section 6.5.2	X	Vital signs only	X	X	Vital signs only	X ^b	X ^b	X ^b	X	X ^b	X ^b	X ^b	X	X ^b	X ^b	X ^b	X	X
Height	Section 6.5.2	X																	
mBMI; NYHA Class; KPS	Section 6.2.5; Section 6.2.11.4 Section 6.2.12	X							mBMI only				mBMI only						X
PND Score	Section 6.2.10		X	X															X
FAP Stage	Section 6.2.10		X – Single assessment at any of these visits																X
Serum Chemistry; Hematology; Urinalysis; Coagulation	Section 6.5.6	X			X				X				X						X

Table 1: Schedule of Assessments – Screening through Treatment Period Month 9

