- The Screening and Baseline visits (V1, V2 and V3) will be performed on separate days and can each occur over multiple days. V2 (first Baseline NIS, mNIS+7, HRdb assessment) must be performed within 21 days prior to the first dose of study drug (Day 1). V3 (second Baseline NIS, mNIS+7, HRdb assessment) must be conducted within approximately 24 hours after Visit 2 but not more than 7 days after. See Section 6.1 for retesting and re-screening instructions.
- Pre-randomization 10-MWT: Two independent assessments will be performed on separate days (1 assessment on each day); the 2 assessments should be performed approximately 24 hours apart from each other but not more than 7 days apart.
- Dosing may be allowed outside of the study center (eg, the patient’s home) under certain circumstances as specified in Section 5.2.2.1 and Section 5.2.2.2. In addition, routine assessments and collection of relevant safety information may be collected outside the study center as specified in the beginning of Section 6.
- LFT for screening: Day 1 predose LFT does not need to be performed if there are available LFT results within 28 days of first dose.
- LFT for after randomization: For the ALN-TTRSC02 cohort, dosing decisions may be made based on LFT results (Table 8) collected at the previous dosing visit (up to 14 weeks prior to dosing); in all cases the most recently available LFTs should be used. LFT monitoring details are provided in Section 5.2.3. For the patisiran cohort, LFTs should be performed according to patisiran visit windows and do not need to be available prior to dosing.

- Unless otherwise specified, assessments on dosing days are predose.
 - For the Month 9, NIS, mNIS+7, HRdb and 10-MWT: Two independent assessments will be performed on separate days (1 assessment on each day); the 2 assessments should be performed approximately 24 hours apart from each other but not more than 7 days apart. Components that are shared between the mNIS+7 and NIS will be performed once at each assessment (eg, the weakness component should not be performed more than once on any given day).

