Patients who discontinue study drug early for any reason during the Treatment Period (defined as the time the first dose of study drug is administered on Study Day 1 through completion of the Month 18 assessments) should complete the Early Drug Discontinuation visit and will be encouraged to remain on the study to complete the modified Month 9 and Month 18 efficacy assessments visits, prioritizing the primary and secondary assessments, where possible so that their experience is captured in the final analyses. If a patient discontinues study drug and completes the Early Drug Discontinuation visit within 3 months of Month 9 or Month 18 and remains on the study, they will not be required to complete the modified efficacy assessments at Month 9 and/or Month 18, as applicable depending on the time they discontinue study drug (Table 3).

Patients who discontinue study drug during the Legacy Treatment Extension Period or the RTE Period will be asked to return to complete the Early Drug Discontinuation visit (Table 3).

Patients who discontinue study drug, but who remain on study, may receive treatment consistent with local standard practice for their disease per Investigator judgment, as applicable. For patients who discontinue study drug and remain in the study, all AEs will be collected for 90 days after the last dose, thereafter, SAEs and AEs of clinical interest (see definition in Section 6.5.7.1) will be collected for the remainder of their participation in the study.

All patients who discontinue study drug will also be asked to complete safety follow-up visits, per the Follow-up Period schedule (see Table 4) until serum TTR levels return to $\geq 80\%$ of baseline (for up to 1 year after the last dose of study drug), or until the patient starts a TTR lowering regimen as a part of clinical care, whichever comes first; all patients will be followed

for a minimum of 3 months. Female patients of child-bearing potential who discontinue ALN-TTRSC02 will be followed until serum TTR levels return to $\geq 80\%$ of baseline.

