6.5.1. Vital Signs

Vital signs will be measured as specified at the timepoints specified in the Schedule of Assessments (Table 1 to Table 4), and include blood pressure, heart rate, body temperature, and respiratory rate. Vital signs will be measured predose, when applicable. When vital signs and blood sample collection occur at the same time, vital signs should be performed before blood samples are drawn, where possible. Vital signs should be measured predose in the seated or supine position, after the patient has rested comfortably for 10 minutes. Blood pressure should be taken using the same arm during a single visit. Body temperature in degrees Celsius will be obtained via oral, tympanic, or axillary methods. Heart rate will be counted for a full minute and recorded in beats per minute, and respiration rate will be counted for a full minute and recorded in breaths per minute.

Additional vital sign assessments, as medically indicated, may be added at the discretion of the Investigator, or as per DMC advice (as applicable).

Vital signs results will be recorded in the eCRF.

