6.5.4. Electrocardiogram

A 12-lead ECG reporting rhythm, ventricular rate, RR interval, PR interval, QRS duration, and QT interval will be obtained locally as specified in the Schedule of Assessments (Table 1 to Table 4).

Triplicate readings should be performed at Baseline and thereafter single readings can be performed.

If the investigator performs an ECG over-read per standard of care, over-reads should be conducted on each individual ECG performed.

Patients should be supine for at least 5 minutes before each ECG is obtained.

When ECG and blood sample collection occur at the same time, ECGs should be performed before blood samples are drawn.

The Investigator or qualified designee will review all ECGs, including those collected by a healthcare professional outside of the study center, to assess whether the results have changed since baseline and to determine the clinical significance of the results. Additional ECGs may be collected at the discretion of the Investigator, or as per DMC advice.

ECG recordings will be archived according to the Study Reference Manual.

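### Section 7.2.8 cuts the safety baseline by calendar day, so applied literally to vital signs it picks the scheduled Day 1 post-dose reading

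*Protocol*

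**What the plan says.** Section 7.2.8 (Safety Analyses) states: "Descriptive statistics will be provided for clinical laboratory data, 12-lead ECG interval data and vital signs data, presented as both actual values and changes from" (the sentence goes on to name the baseline as the reference). The next paragraph covers laboratory shift tables and then gives the definition: "Baseline will be defined as the last observation on or prior to Study Day 1". No other baseline definition appears in that section.

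Section 4.3.1 starts the Treatment Period at "the time the first dose of study drug is administered on Study Day 1", so Study Day 1 contains both untreated and treated time.

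Table 1 (Schedule of Assessments, Screening through Month 9) splits Day 1 into a pre-dose and a post-dose column. In the row for vital signs and weight, the pre-dose cell is marked and the post-dose cell reads "Vital signs only". The Table 1 notes add: "Unless otherwise specified, assessments on dosing days are predose".

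Section 6.5.1 says: "Vital signs will be measured predose, when applicable". Section 6.1 has the remaining baseline assessments done at Visit 3 or on Day 1 ahead of the first dose.

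**The concern.** A baseline for change scores should precede treatment. This rule sets the boundary at the end of a day on which treatment starts, and the schedule asks for a vital-sign reading after treatment on that same day. The last observation on or before Day 1 is then a treated one.

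Two things would follow. An acute effect of the first dose on blood pressure, heart rate, temperature or respiratory rate could not show in the Day 1 change, because the post-dose reading would be compared with itself. Every later change would also be measured from a shifted starting point.

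The arms are not handled alike on Day 1. Section 5.2.2.2 gives patisiran as an infusion preceded by a corticosteroid, paracetamol and H1 and H2 blockers, and Section 1.7 names infusion-related reactions as an identified risk of patisiran. ALN-TTRSC02 is a subcutaneous injection without premedication. Any shift could therefore differ between the two arms shown side by side.

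**Working it through.** The protocol states no figure here to reproduce. The check is to align the schedule row, apply the rule to the scheduled readings, and trace the result algebraically.

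**Step 1: does the post-dose cell belong to Day 1?** Table 1 has 18 visit columns: V1, V2, V3, Day 1 pre-dose, Day 1 post-dose, twelve visits from D22 to D253, and the Month 9 efficacy visit (3 + 2 + 12 + 1 = 18). The vital signs and weight row has 18 entries, so they map one to one:

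| Column | Entry |
|---|---|
| V1 | marked |
| V2 | vital signs without weight |
| V3 | marked |
| Day 1 pre-dose | marked |
| Day 1 post-dose | vital signs without weight |
| D22 onward | marked |

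As a cross-check, the entries between D22 and D253 that lack the pandemic deferral footnote fall on D85, D169 and D253, which are the ALN-TTRSC02 dosing visits. The alignment is right. The original protocol's Table 1 maps the same way and has the same pair of Day 1 entries.

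**Step 2: apply the rule.** The scheduled vital-sign readings in time order are V1, V2, V3, Day 1 pre-dose, Day 1 post-dose, D22.

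- Last reading with study day at or before 1: Day 1 post-dose.
- Last reading before the first dose: Day 1 pre-dose.

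**Step 3: trace the effect.** For one patient, let Y0 be the Day 1 pre-dose value, Y1 = Y0 + d the Day 1 post-dose value, and Yt a later value.

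- Day 1 post-dose change: the true value is Y1 - Y0 = d; under the rule it is Y1 - Y1 = 0.
- Later change: the true value is Yt - Y0; under the rule it is Yt - Y1 = (Yt - Y0) - d.
- Difference between arms in mean later change, with mean shifts dA (ALN-TTRSC02) and dP (patisiran): the true difference minus (dA - dP). The error cancels only if both arms shift equally.

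**Step 4: who and what is touched.** With about 160 patients randomised 3:1, the planned arms are 160 × 3/4 = 120 and 160 × 1/4 = 40. Every patient with a Day 1 post-dose reading is affected. Weight is not, because the post-dose cell excludes it. Day 1 chemistry, hematology, urinalysis, coagulation and LFT samples are scheduled pre-dose only, so both rules give the same laboratory baseline. Section 7.2.8 already counts adverse events from the first dose, so those tables do not depend on the rule.

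**The case against.** The strongest reply is that the protocol makes its pre-dose intent plain elsewhere. Section 6.1 puts baseline assessments ahead of the first dose, Section 6.5.1 calls for pre-dose vital signs, and the Table 1 notes make pre-dose the default on dosing days. The definition also directly follows the laboratory shift-table sentence and may have been meant for laboratory data only, where it does no harm. The SAP, which was not available for this review, may settle the matter.

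Much of this stands as evidence of intent. It does not remove the conflict. Sections 6.1 and 6.5.1 govern when measurements are taken and do not restate the analysis definition. The Table 1 default gives way where something else is specified, and a post-dose column specifies it. The sentence is not limited to laboratory data, and no other definition serves the vital-sign changes called for in the same section. Section 7 says the SAP implements the protocol's principal features, and here the protocol states a rule, so this is more than a detail left for later.

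Two stronger readings are tempting, and the documents support neither.

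- A reader might infer that the randomised safety comparison is biased. Safety data are only summarised descriptively, actual vital-sign values are reported beside the changes, and acute reactions are also captured as adverse events. At most, one set of descriptive change summaries is distorted.
- A reader might infer that the rule reduces the ECG baseline to a single tracing. Section 6.5.4 says: "Triplicate readings should be performed at Baseline and thereafter single readings can be performed". Nothing says only one of the three will be used, and averaging triplicates is a derivation convention normally left to the SAP. No loss of ECG precision can be claimed.

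**Conclusion.** The point holds as a conflict between a stated rule and the schedule. Applied to vital signs as written, Section 7.2.8 takes the Day 1 post-dose reading as baseline, against the protocol's own pre-dose intent.

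The consequence is modest: descriptive vital-sign changes that miss the first-dose shift and are off by -d afterwards, possibly by different amounts in the two arms. The size of d appears nowhere in the protocol and may be small.

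The conclusion assumes that the definition covers all change-from-baseline summaries in its section and that the post-dose readings are taken as scheduled. If the sentence was meant for laboratory data alone, then the vital-sign changes have no stated definition and the same clarification is needed.

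**What to change.** In Section 7.2.8, define baseline as the last non-missing observation before the first dose of study drug. Add that Day 1 post-dose vital signs are summarised as a post-baseline time point. Carry the same definition into the SAP.

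The cost is one sentence and a matching line in the SAP. Data collection and the visit schedule do not change, and baselines for assessments scheduled only before dosing stay as they are. The first-dose vital-sign change, which the present wording would show as zero, becomes visible.

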7.2.9. Immunogenicity Analyses

Incidence of ADA and titers will be summarized descriptively.

7.2.10. Other Analyses

Not applicable.

7.2.11. Interim Analysis

No interim analysis is planned.

8. STUDY ADMINISTRATION

8.1. Ethical and Regulatory Considerations

This study will be conducted in accordance with the protocol, all applicable regulatory requirements, and the current guidelines of Good Clinical Practice (GCP). Compliance with GCP provides public assurance that the rights, safety, and well-being of study patients are protected consistent with the principles that have their origin in the Declaration of Helsinki.

8.1.1. Informed Consent and Medical Records Release Form

The Investigator will ensure that the patient/legal guardian is given full and adequate oral and written information about the nature, purpose, possible risk and benefit of the study. Patients/legal guardians must also be notified that they are free to discontinue from the study at any time. The patient/legal guardian should be given the opportunity to ask questions and allowed time to consider the information provided.

The Investigator will inform the patient/legal guardian if new information becomes available that may be relevant to the patient's/legal guardian's willingness to continue participation in the study. Communication of this information should be documented.

The patient's/legal guardian's signed and dated informed consent must be obtained before conducting any study tests or procedures that are not part of routine care.

The Investigator must maintain the original, signed ICF. A copy of the signed ICF must be given to the patient/legal guardian.

In addition of the ICF, patients will be asked to sign a Medical Records Release Form (where allowed by local regulations) at Screening for the purpose of obtaining information on vital status, cardiac transplant procedures, left-ventricular assist device placement (Section 6.2.8), and hospitalizations (Section 6.2.7) from patients for the duration of the study. This information will be obtained by the patient's physician through contacting the patient or family or from death registries.

Signing the Medical Records Release Form will be optional and will apply if the patient discontinues from the study early. The form should be checked at the Early Treatment

Discontinuation Visit and a new form will be signed if the information needs updating. Every effort should be made to collect the Medical Records Release Form from all patients enrolled in the study.

8.1.2. Ethical Review

The study protocol, including the ICF (assent form, if applicable), must be approved or given a favorable opinion in writing by an IRB or IEC, as appropriate. The Investigator must submit written approval before he or she can enroll any patient into the study.

The Investigator is responsible for informing the IRB or IEC of any amendment to the protocol in accordance with local requirements. In addition, the IRB or IEC must approve all patient materials for the study (except those that support the need to remove an apparent immediate hazard to the patient). The protocol must be reapproved by the IRB or IEC upon receipt of amendments and annually, as local regulations require.

Initial IRB or IEC approval of the protocol, and all materials approved by the IRB or IEC for this study including the patient consent form and recruitment materials must be maintained by the Investigator and made available for inspection.

The Investigator will submit reports of SAEs as outlined in Section 6.5.7. In addition, the Investigator agrees to submit progress reports to the IRB or IEC per their local reporting requirements, or at least annually and at the conclusion of the study. The reports will be made available to the Sponsor or designee.

Any communications from regulatory agencies, IRBs, or IECs in regard to inspections, other studies that impact this protocol or the qualifications of study personnel should be promptly reported to the Sponsor or its designee.

The Investigator is also responsible for providing the IRB or IEC with reports of any reportable serious adverse drug reactions from any other study conducted with the study drug. The Sponsor or designee will provide this information to the Investigator.

Major changes in this research activity, except those to remove an apparent immediate hazard to the patient, must be reviewed and approved by the Sponsor and the IRB or IEC that approved the study. Amendments to the protocol must be submitted in writing to the Investigator's IRB or IEC and the Regulatory Authority for approval before patients are enrolled or randomized under the amended protocol, and patients must be re-consented to the most current version of the ICF.

8.1.3. Serious Breach of Protocol

Investigators must notify the medical monitor within 24 hours of becoming aware of a potential serious breach of the protocol. A serious breach is a breach that is likely to affect to a significant degree the safety and rights of a study participant or the reliability and robustness of the data generated in the clinical trial.

8.1.4. Study Documentation, Confidentiality, and Records Retention

All documentation relating to the study should be retained for 2 years after the last approval in an ICH territory or as locally required, whichever is longer. If it becomes necessary for the Sponsor, the Sponsor's designee, applicable IRB/IEC, or applicable regulatory authorities to

review or audit any documentation relating to the study, the Investigator must permit direct access to all source documents/data. Records will not be destroyed without informing the Sponsor in writing and giving the Sponsor the opportunity to store the records for a longer period of time at the Sponsor's expense.

The Investigator must ensure that the patients' confidentiality will be maintained. On the eCRFs or other documents submitted to the Sponsor or designees, patients should not be identified by their names, but by the assigned patient number or code. If patient names are included on copies of documents submitted to the Sponsor or designees, the names will be obliterated and the assigned patient number added to the document. Documents not for submission to the Sponsor (eg, signed ICFs) should be maintained by the Investigator in strict confidence.

The Investigator must treat all of the information related to the study and the compiled data as confidential, whose use is for the purpose of conducting the study. The Sponsor must approve any transfer of information not directly involved in the study.

To comply with local and/or regional regulations, this clinical study may be registered and study results may be posted on public registries, such as ClinicalTrials.gov.

